## **Statistical Analysis**

### **Power Analysis**

We define an equivalent mean pain score to be a margin of one point in either direction on the eleven-point NRS scale. Based on retrospective quality improvement data at our institution, the patient-reported surgical site pain on the eleven point NRS scale following THA in patients who received a preoperative LPB at Davie Medical Center had a mean of 4.8 and standard deviation of 2.0. Using these values, and setting the significance level to 0.05 with a power of 80%, we calculated the minimum required sample size to be  $n=69$  in the LPB group and  $n=69$  in the PENG group to conclude equivalence of movement pain at six hours between the two groups. Power was calculated using the R package 'TOSTER'. We intend to recruit  $n=80$  patients per arm to allow for attrition and dropout.

### **Data Analysis**

Demographic information will be collected and compared between the groups to verify that randomization balanced out important baseline variables between LPB and PENG. For the primary outcome of patient-reported pain with movement at six hours after block placement, the equivalence hypothesis test of LPB versus PENG groups will be performed using two one-sided t-tests. We will also calculate a point and confidence interval estimate of the difference between LPB and PENG groups. Secondary outcomes will also be compared using t-tests and confidence intervals.

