### **Selection Criteria**

Inclusion: Adults between 18 and 90 years of age undergoing elective primary total hip arthroplasty surgery by an anterior approach at Atrium Health Wake Forest Baptist Davie Medical Center, and who have consented to and lack any contraindications to either LPB or PENG block for postoperative analgesia will be recruited for participation in the study.

Exclusion: Patients with any contraindications to regional anesthesia, such as history of allergy to amide local anesthetics, pre-existing coagulopathy or thrombocytopenia (less than 100,000 per microliter), refusal to either analgesic block, presence of a progressive lower extremity neurological deficit, localized or systemic infection, chronic use of high dose opioid analgesics (defined as daily use greater than 60mg oxycodone equivalents), as well as those who are pregnant, will be excluded from participation. A diagnosis of multiple sclerosis and Parkinson's disease will also exclude potential study subjects. Any patients who refuse enrollment or withdraw their consent will be excluded and any of their information already collected will be destroyed.

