### **Setting**

Patients between 18 and 90 years of age, scheduled to undergo elective, primary total hip arthroplasty surgery at Davie Medical Center performed by the two orthopedic surgeons who perform THA by an anterior approach at our institution, will be identified for eligibility. These patients will be seen in the preoperative assessment clinic per our standard protocol prior to their surgery date, at which time the study will be discussed with all eligible patients, and they will be offered the ability to enroll in the study. Written informed consent will either be obtained during this visit, or the patient will be allowed to take the consent form home with them to discuss with their family and consider participation, and written informed consent can be finalized on the day of surgery.

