## **Study Protocol**

### **Baseline data collection**

Upon arrival and check-in to the regional anesthesia area of surgical services at Davie Medical Center on the day of surgery, enrolled patients will be asked to rate their baseline verbal pain score both at rest and with movement on the eleven-point NRS pain scale (0-10, where 0 represents no pain and 10 represents the worst imaginable pain). Patient characteristics will be recorded, including age, gender, height, weight, BMI, surgeon, and operative side, as well as preoperative opioid use and doses. Baseline motor function will be assessed by straight leg raise on the surgical side to resistance and measured on the six-point Medical Research Council (MRC) scale (0-5, where 0 represents no voluntary contraction possible, 1 represents muscle flicker without movement of limb, 2 represents active movement only with gravity eliminated, 3 represents movement against gravity but without resistance, 4 represents movement possible against some resistance, and 5 represents normal motor strength against resistance).

Two phone numbers will be obtained from the patient, if the patient consents, for contact after discharge. Each patient will also be provided with a pain journal with which to document pain scores for any remaining time points after discharge, in case they are not available by phone at the time points of interest. All patients will still be admitted at the six hour mark, for collection of the primary endpoint of NRS pain with movement, as well as motor strength at six hours after block placement.

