### **Randomization**

Prior to beginning any regional anesthesia procedures, each patient will be randomized to one of the aforementioned treatment arms consisting of LPB or PENG block by research personnel and/or the attending anesthesiologist in charge of the patient's care. Randomization will occur in blocks of sequentially numbered opaque envelopes. Patients will be blinded to their treatment arm assignment, as will all research personnel who collect outcome data. Patient blinding will occur through the use of a sham block procedure as detailed below.

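### The primary equivalence test ignores the baseline movement-pain score the trial already collects; pre-specified adjustment could add power at little cost

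*Combined protocol and SAP*

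**What the plan says.** The Data Analysis section states that "the equivalence hypothesis test of LPB versus PENG groups will be performed using two one-sided t-tests", with a point estimate and confidence interval for the difference. It names no covariate. Its only stated use of baseline data is a comparison between arms to check balance, and it does not say what follows if the arms turn out unbalanced.

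Under Baseline data collection, "enrolled patients will be asked to rate their baseline verbal pain score both at rest and with movement", on the same 0–10 scale as the primary outcome. That section also records "surgeon, and operative side, as well as preoperative opioid use and doses". The Setting section refers to "the two orthopedic surgeons who perform THA by an anterior approach at our institution". Selection Criteria exclude "daily use greater than 60mg oxycodone equivalents", so opioid use up to that level is allowed. On allocation, "Randomization will occur in blocks of sequentially numbered opaque envelopes"; no stratification is mentioned.

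The only model elsewhere in the plan is the mixed-effects model under Missing Data Points. It applies only if substantial parts of the repeated measurements are missing, it lists the 6, 12, 18 and 24 hour scores, and it names no covariate.

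**The concern.** Equivalence is shown only if the whole 90% confidence interval for the difference lies between −1 and +1, so the width of the interval decides success. If baseline movement pain predicts six-hour movement pain, adjusting for it removes part of the residual variance and narrows the interval. It also removes the shift in the estimate that chance baseline imbalance causes. The t-test's error rates already allow for that shift, so this is a matter of precision and not of bias.

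There is a secondary point. A balance check with no stated consequence leaves room for a decision on adjustment after the data have been seen. A model named in advance closes that gap.

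**Working it through.** **Inputs.** From Power Analysis: margin ±1, SD 2.0, significance level 0.05, power 80%, 69 per arm required, 80 per arm recruited. A true difference of 0 is assumed; it is the value that reproduces the plan's figure. The correlation r is not in the documents and is varied from 0 to 0.5.

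**The plan's own figure.** With 0.05 for each one-sided test, the normal approximation is

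n = 2 × [SD × (z₀.₉₅ + z₀.₉₀) / margin]² = 2 × [2.0 × (1.645 + 1.282) / 1]² = 68.5, rounded up to 69.

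The plan's 69 is reproduced. Exact power, integrating over the distribution of the pooled variance, is 79.9% at 69 per arm and 86.7% at 80 per arm; exactly 80% needs 70.

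**Effect of adjustment.** The residual SD becomes 2.0 × √(1 − r²), for example 1.91 at r = 0.3 and 1.73 at r = 0.5. The cost has two parts:
- One degree of freedom is lost, which costs under 0.1 point of power.
- Chance correlation between covariate and arm inflates the standard error by 1/√(1 − R²), where R² comes from regressing arm on k covariates and follows Beta(k/2, (2n − 1 − k)/2). Power is averaged over this distribution.

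Net exact power, adjusting for baseline movement pain only (k = 1):

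| r | 69 per arm | 80 per arm |
|---|---|---|
| Unadjusted | 79.9% | 86.7% |
| 0 | 79.5% | 86.5% |
| 0.1 | 80.0% | 86.9% |
| 0.2 | 81.5% | 88.1% |
| 0.3 | 84.1% | 90.0% |
| 0.4 | 87.4% | 92.5% |
| 0.5 | 91.4% | 95.2% |

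Break-even is at about r = 0.09 at 69 per arm and 0.08 at 80. A simulation of 20,000 trials at 69 per arm agrees: 80.0% unadjusted, 79.5% adjusted at r = 0, 84.1% adjusted at r = 0.3.

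**Sample size for 80% power, net of the cost:** 70, 70, 67, 64, 59 and 53 per arm for r = 0, 0.1, 0.2, 0.3, 0.4 and 0.5.

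**Interval width.** The 90% half-width at 69 per arm is about 1.66 × 2.0 × √(2/69) = 0.56 unadjusted. It is 0.54 at r = 0.3 and 0.49 at r = 0.5, before the small inflation from chance covariate–arm correlation.

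**Chance imbalance.** The 95% range of the shift in the unadjusted estimate at 69 per arm is ±1.96 × r × 2.0 × √(2/69): ±0.07 at r = 0.1, ±0.20 at r = 0.3, ±0.33 at r = 0.5.

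**Three covariates.** If surgeon and opioid dose are added and predict nothing, net power at 69 per arm is 78.7, 79.2, 80.8, 83.4, 86.8 and 90.9% for r = 0 to 0.5. Break-even rises to about r = 0.15 (0.14 at 80 per arm). At r = 0 the loss is 79.9 − 78.7 = 1.2 points at 69 per arm and 86.7 − 85.9 = 0.8 at 80. Simulation at 69 per arm gave 78.4% against the calculated 78.7%; its standard error is √(0.8 × 0.2 / 20,000) = 0.28 points, so the two agree.

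**Non-zero true difference.** If the true difference were 0.25 points (an assumption), power at 69 per arm would be 68.5% unadjusted, 72.5% adjusted at r = 0.3 and 80.4% adjusted at r = 0.5.

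**The case against.** The plan is coherent as it stands: an unadjusted sample size supports an unadjusted test, and no section contradicts another. The case for change rests on a correlation that the documents do not supply, and a low value is plausible. The covariate is pain in the hip before surgery. The outcome is pain six hours after a block, following surgery under spinal anesthesia, with scheduled analgesics and opioids as needed. At r = 0.1 the net gain is 0.1 to 0.2 points of power; at r = 0.2 it is 1.6 points at 69 per arm and 1.4 at 80. The row for 80 per arm may also be the fairer one, since all patients are expected to be in hospital at six hours. Adding surgeon and opioid dose can lose power.

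All of this stands, and it limits the point to an optional improvement. It does not remove it. With baseline pain as the only covariate the possible loss is about 0.4 points, against gains of 4.2 to 11.5 points at 69 per arm (3.3 to 8.5 at 80) if r is 0.3 to 0.5. The point about the extra covariates is a reason to treat them as optional.

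One could also ask whether baseline pain is scored before allocation. The order of the sections implies it but does not state it; the protocol says that "Prior to beginning any regional anesthesia procedures, each patient will be randomized to one of the aforementioned treatment arms". Since "Patients will be blinded to their treatment arm assignment, as will all research personnel who collect outcome data", a score taken before the block is a usable covariate either way.

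**Conclusion.** The point holds as a missed efficiency, worth considering. The unadjusted test is valid and 69 per arm is right for it. Adjusting for baseline movement pain costs at most about 0.4 points of power and pays once r exceeds about 0.09. The gain is under 2 points for r up to 0.2 and becomes material from about r = 0.3. These figures assume SD 2.0, a true difference of 0 and a linear relation between baseline and six-hour scores. The size of r is unknown, so the size of the gain is too. No gain is claimed for surgeon or opioid dose.

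**What to change.** Before any unblinded analysis, amend the Data Analysis section as follows.

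- Primary analysis: ANCOVA of six-hour movement pain on arm and baseline movement pain. Declare equivalence if the 90% confidence interval for the adjusted difference lies within (−1, +1).
- Optional covariates: surgeon as a factor and preoperative opioid dose (mg oxycodone equivalents per day, linear), only if named now and with the r = 0.15 break-even in mind. Baseline pain alone is the safer choice.
- Missing baseline score: replace it with the mean pooled over both arms, so that no patient is dropped.
- Sensitivity analysis: the unadjusted two one-sided t-tests.
- For consistency, adjust later movement scores for baseline movement pain and rest scores for baseline rest pain, and put the same terms in the mixed model under Missing Data Points. No gain has been quantified for these. The 0–5 motor grade is not part of this change.
- State in the protocol that baseline scores are recorded before the envelope is opened.

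The change is to wording only: every covariate is already collected and the sample size stays as planned. The statistical cost is at most about 0.4 points of power at 69 per arm with baseline pain alone, or 1.2 points with all three covariates if none is predictive.

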**Objectives**

The purpose of this randomized, double blinded, prospective study is to compare the postoperative analgesia provided by the PENG block to that provided by the LPB for patients undergoing primary anterior approach THA. We hypothesize that the PENG block will provide equivalent analgesia to LPB after THA. The primary outcome will be a comparison of patient-reported numeric rating scale (NRS) pain scores with movement at six hours following block placement. Equivalency will be defined as a difference of less than one point in either direction on the eleven-point NRS pain scale (0-10). Secondary outcomes will include NRS pain scores with movement at 12, 18, and 24 hours, NRS pain scores at rest at 6, 12, 18, and 24 hours, time to first opioid administration, cumulative dose of postoperative opioid administration within the first 24 hours, motor strength at six hours after block placement as assessed by straight leg raise on a six-point scale (0-5), and distance walked at first postoperative physical therapy session. The 18 hour assessment for pain at rest and with movement is allowed to be done retrospectively at the time of the 24 hour assessment, as this time point would end up interrupting the sleep of the study subject as would be occurring in the early morning hours. If the subject reports asleep

at the 18 hour scheduled time point, the no pain score will be obtained. This will be considered a missing data point and not a deviation. If the subject reports they were awake at the 18 hour time point, then a pain score at rest will be obtained but if the subject reports no movement, this score will be a missing data point and not a deviation.

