side up (standard at our institution, as we use an isobaric spinal solution). Using a skin marker, midline will be marked on their lumbar spine at the level of the iliac crests, and a point two thirds the distance between midline and the posterior superior iliac spine on the surgical side will be marked. Following this, their lower back areas will be prepared with antiseptic solution and draped in sterile fashion. All subjects will then receive a skin wheal with 1cc of 1% lidocaine at the standard LPB block site just marked as described above. Those subjects assigned to the LPB treatment arm will subsequently receive a stimulation-based LPB dosed with 20cc of 0.2% ropivacaine with 1:400,000 dilution epinephrine dosed in 5mL increments with negative aspiration beforehand and between each aliquot. The PENG block site skin wheal will behave as a sham block for subjects enrolled in the LPB arm, and the LPB block site skin wheal will behave as a sham block for those enrolled in the PENG arm.

All patients will then receive a spinal block as the primary anesthetic using 3.5mL of 0.5% ropivacaine with 10mcg fentanyl. Following placement of the spinal block, the patients will be brought to the operating room and receive our standard intraoperative protocol of propofol infusion for sedation, along with dexamethasone 10mg IV, ondansetron 4mg IV, surgical antibiotic prophylaxis as appropriate, and IV tranexamic acid 1g at both capsule opening and capsule closure. Any patients whose spinal block are determined to have failed, as checked prior to initiation of propofol sedation and surgical skin preparation with a pinch test on the surgical lower extremity, will be induced under general anesthesia using propofol with placement of a laryngeal mask airway or endotracheal tube at the discretion of the attending anesthesiologist.

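### The equivalence test has no supporting analysis for patients who did not receive the assigned block, and block delivery is not a listed study variable, so undelivered or crossed-over blocks could ease a false equivalence claim.

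*Combined protocol and SAP*

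**What the plan says.** All places are in the combined protocol and SAP.

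- **Objectives.** The hypothesis is equivalent analgesia, judged on movement pain at six hours. "Equivalency will be defined as a difference of less than one point in either direction on the eleven-point NRS pain scale (0-10").
- **Data Analysis.** For the primary outcome, "the equivalence hypothesis test of LPB versus PENG groups will be performed using two one-sided t-tests", with a point estimate and a confidence interval. No intention-to-treat, as-treated or per-protocol set is named, and no sensitivity analysis covers departures from the assigned block.
- **Randomization and Interventions.** Allocation precedes any block. In the lumbar plexus arm, "Those subjects assigned to the LPB treatment arm will subsequently receive a stimulation-based LPB dosed with 20cc of 0.2% ropivacaine"; the PENG arm has a corresponding injection, and each arm has a skin wheal as sham at the other site. No check of study-block success and no replacement block is described. Failure of the spinal is checked, and those patients "will be induced under general anesthesia using propofol with placement of a laryngeal mask airway or endotracheal tube".
- **Baseline data collection and Measurements.** Whether the assigned block was completed, abandoned or replaced is not among the listed data. Medication administration is charted in the EMR.
- **Reporting of Unanticipated Problems, Adverse Events, or Deviations.** Attending anesthesiologists report protocol violations to the principal investigators. No link to an analysis variable is given.
- **Missing Data Points.** This section deals only with missing longitudinal measurements.

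**The concern.** In a superiority trial, patients who do not receive their assigned treatment usually make the result conservative. In an equivalence trial the same dilution can work towards the claim. If some patients receive the other arm's block, or if similar shares of both arms receive no full block, a real difference between the blocks appears smaller and the interval fits within ±1 more easily. The 5% error rate still holds for the comparison of randomized groups, but not for the comparison of the blocks as delivered, which is what a reader will take from a statement that PENG and lumbar plexus block are equivalent.

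A per-protocol analysis is the usual safeguard, and it needs delivery data. The abstractors of outcome data are blinded to allocation, and the Confidentiality and Privacy section has identifiers destroyed as early as is practicable, leaving an anonymous data set. Reconstructing block delivery afterwards could therefore be difficult. With no rule written down, the handling of such patients would also be open to choice after the data are seen.

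**Working it through.** **Inputs from the plan.** Margin 1 point (Objectives). From Power Analysis: lumbar plexus pain scores "had a mean of 4.8 and standard deviation of 2.0"; "setting the significance level to 0.05 with a power of 80" per cent; "we calculated the minimum required sample size to be" 69 per arm; and recruitment of 80 "patients per arm to allow for attrition and dropout".

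**1. The plan's sample size.** For two one-sided tests with true difference 0:

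n = 2 × [SD × (z0.95 + z0.90) / margin]² = 2 × [2.0 × (1.645 + 1.282) / 1]² = 68.51, so 69 per arm.

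Exact power with the t distribution is 79.9% at 69 and 86.7% at 80 per arm. The stated figure reproduces and is not in question.

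**2. False equivalence under dilution.** Equivalence is declared when |D| < 1 − t(0.95, 2n−2) × S × √(2/n), where D is the observed difference and S the pooled SD. Suppose the delivered blocks truly differ by 1.0 and a share f of the contrast is lost, so the randomized groups differ by 1 − f. This is the result if f of one arm has the other block's outcome, or if f of both arms has no block and the same mean pain.

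By hand for n = 80 and f = 10%: the standard error is 2.0 × √(2/80) = 0.316; the limit for |D| is 1 − 1.655 × 0.316 = 0.477; (0.477 − 0.90)/0.316 = −1.34, a probability of about 9.0%. Averaging over the sampling variation of S gives 9.2%.

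| Contrast lost (assumed) | Remaining difference | 69 per arm | 80 per arm |
|---|---|---|---|
| 0% | 1.00 | 5.0% | 5.0% |
| 5% | 0.95 | 6.7% | 6.8% |
| 10% | 0.90 | 8.8% | 9.2% |
| 20% | 0.80 | 14.4% | 15.5% |

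If a share f crosses over in each arm, the loss is 2f, so 5% crossover in both arms corresponds to the 10% row and 10% to the 20% row.

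**3. Direction.** Assume means of 4.8 (lumbar plexus), 5.8 (PENG) and 7 (no block delivered), with the SD widened for the mixture and 80 per arm. The last two means are illustrative.

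- 10% non-delivery in both arms: 5.92 − 5.02 = 0.90; false equivalence 9.0%.
- 10% in the lumbar plexus arm only: 5.80 − 5.02 = 0.78; 16.6%.
- 10% in the PENG arm only (here the worse arm): 5.92 − 4.80 = 1.12; 2.2%.

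**4. Conversion to general anesthesia.** Assume 5% conversions in each arm, each adding 2 points. The difference is unchanged and the SD becomes √(4 + 0.05 × 0.95 × 2²) = 2.05. With 80 per arm, false equivalence stays at 5.0% and power at true equality falls from 86.7% to 84.8%.

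**5. Power in a per-protocol set.** Starting from 80 per arm, true difference 0, SD 2.0:

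| Total loss per arm | Patients left | Power |
|---|---|---|
| 5% | 76 | 84.5% |
| 10% | 72 | 82.0% |
| 13.75% (11 of 80) | 69 | 79.9% |
| 15% | 68 | 79.1% |
| 20% | 64 | 75.7% |

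Requiring both tests to pass costs a little more. By simulation, with all 80 per arm in the as-randomized test, joint power is about 83% with 4 per arm excluded from the per-protocol set and about 78% with 11 excluded.

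**The case against.** The best defence is that the documents describe no crossover. Each patient has one assigned block and one sham in a fixed sequence, performed by experienced faculty or by a directly supervised fellow, and lumbar plexus block is long-standing practice at the institution. The natural reading of the compared groups is the randomized groups, for which the test keeps its 5% level. At 5% dilution the rate moves only from 5.0% to 6.8%, and only if the true difference lies exactly at the margin. All of this stands. It limits the size of the concern but does not supply the missing supporting analysis.

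Four stronger readings are tempting and are not supported:

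- *Failed blocks always pull the arms together.* They do not: non-delivery mainly in the worse arm widens the difference (step 3).
- *Conversion to general anesthesia produces false equivalence.* Conversion follows failure of the spinal, which both arms receive. At equal rates and effects it adds variance and makes equivalence harder to show (step 4).
- *There is no record of what was given.* Violations are reported and medication is charted. What is missing is a listed study variable tied to the analysis.
- *The spare 11 patients per arm can absorb per-protocol exclusions at no cost.* The plan has already allotted them to attrition.

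It is also fair to say that a per-protocol set does not remove a full injection that simply works poorly. That is proper: poor effect of a delivered block is part of what is being compared.

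**Conclusion.** The concern holds in a limited form. The plan has one equivalence test, no supporting analysis for patients who did not receive the assigned block, and no listed variable from which to build one. Crossover, or non-delivery at similar rates in both arms, would raise the chance of a false claim at the margin from 5.0% to about 6.8%, 9.2% or 15.5% for a 5%, 10% or 20% loss of contrast. These figures rest on the plan's SD and margin, 80 analysed per arm, a true difference of exactly 1.0 and assumed loss rates. The sample size is sound. This is an inexpensive improvement that should be made; it does not show that the primary test is invalid.

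**What to change.** In Data Analysis:

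1. State that the primary test compares patients as randomized.
2. Add the same two one-sided tests in a prespecified per-protocol set that excludes patients who did not receive the full assigned injection or who received the other block before the six-hour score.
3. Claim equivalence without qualification only if both 90% confidence intervals, which correspond to tests at 0.05 per side, lie within ±1. The per-protocol analysis supports the randomized comparison and does not replace it, because its exclusions occur after randomization and may be related to prognosis.
4. Keep conversions to general anesthesia in the per-protocol set, since they are care specified by the protocol. Record them and, if wanted, examine them in a separate sensitivity analysis.

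On the data form, have the unblinded anesthesiologist record on the day whether the assigned block was completed, the volume given and any other block given, with its time. Report these by arm, since the direction of any bias depends on where the departures fall.

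The cost is a few form items, one repeat of a planned test and a claim that is slightly harder to reach, as in step 5. The losses shown there must cover attrition as well as per-protocol exclusions; beyond 11 per arm in total, per-protocol power falls below that of the plan's 69 per arm.
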